Adverse Event	Any untoward or unfavorable medical occurrence associated with the subject's participation in the research, whether or not considered related to the subject's participation in the research (Section 8.2.1)
Allograft Dysfunction	An unexplained elevation in ALT or GGT tests relative to baseline; \geq 2-fold the ULN (based on Harrison's Principles of Internal Medicine, 18 th edition) if the baseline value was $<$ than the ULN; or, \geq 2-fold the baseline value if the baseline value was \geq than the ULN (Section 6.6.1)
Baseline Liver Function Test	The average of two LFTs taken at the following times: LFT taken at screening; and LFT taken 7 (+/- 2 days) before initiation of immunosuppression withdrawal. See Section 6.6.1 for details.
Enrollment	The signing of informed consent. (Section 3.1.1)
Failed immunosuppression withdrawal	Participants with a biopsy that is positive or suspicious for rejection, participants with presumed rejection who are unable to undergo a biopsy, participants who exceed 45 weeks to complete immunosuppression withdrawal, or participants who demonstrate any of the histological findings in Table 1 on their biopsy performed 52 weeks following discontinuation of all immunosuppression (Sections 3.1.3.5 and 6.9).
Hepatitis C Virus	Presence of HCV confirmed by a positive HCV antibody test (Section 4.2.1)
Intent-to-Treat Sample	All participants who provide informed consent for study participation and begin immunosuppression withdrawal (Section 9.1)
Liver Function Tests	Includes direct bilirubin, ALT and GGT.
Liver Function Test ULN values	Value ranges are according to the Harrison's Principles of Internal Medicine, 18 th edition (ALT: 41 U/L; GGT 58 U/L; Direct Bilirubin: 0.4 mg/dL) (Section 4.1)
Operational Tolerance	No evidence of rejection since enrollment in the study, a liver biopsy at 52 weeks following discontinuation of all immunosuppression demonstrating absence of rejection per the Banff global assessment criteria and histological stability consistent with operational tolerance per Banff 2012, defined as the absence of histological findings in Table 1 (Section 3.3.1)
Per Protocol Sample	All participants who attempt immunosuppression withdrawal and do not have any unacceptable major protocol deviations (Section 9.1)
Screen Failure	Enrolled participants who do not fulfill eligibility criteria or who do not initiate immunosuppression withdrawal for any reason (Section 3.1.1)

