3.3 STUDY ENDPOINTS

3.3.1 Primary Endpoint

The primary endpoint is the proportion of participants who achieve operational tolerance 52 weeks after completion of immunosuppression withdrawal defined by:

- No evidence of rejection since enrollment in the study.
- A liver biopsy at 52 weeks following discontinuation of all immunosuppression demonstrating absence of rejection per the Banff global assessment criteria¹⁻³. The central pathology read will be used for this determination.
- A liver biopsy at 52 weeks following discontinuation of all immunosuppression demonstrating histological stability consistent with operational tolerance per Banff 2012 criteria⁴, defined as the *absence* of the histological findings in **Table 1**. The central pathology read will be used for this determination.

For the purposes of evaluating donor-specific exhaustion, operationally tolerant participants will be compared to those who fail immunosuppression withdrawal.

Table 1. Follow-Up Biopsy Findings Suggesting that Patients are Unlikely to Benefit from Minimal or No IS*

COMPARTMENT	FINDINGS
Portal inflammation and interface activity	Increased portal inflammation (in comparison with a pre-weaning biopsy sample), especially in association with histopathological evidence of tissue damage manifest as: focally worsening or more prevalent lymphocytic bile duct damage, interface hepatitis, fibrosis, or the appearance of definite venous endotheliitis.
Centizonal / perivenular inflammation	New onset perivenular inflammation (in comparison with a pre-weaning biopsy sample) associated with even mild perivenular necro-inflammatory activity. Note: these changes might be present in the absence of typical portal changes of rejection.
Bile duct changes	New-onset biliary epithelial cell senescence changes or ductopenia when sampling problems and/or an alternative, non-immunological explanation (e.g. biliary strictures) can be reasonably excluded
Fibrosis**	Greater than 1 grade increase in fibrosis in any one compartment: (a) portal/periportal; (b) peri-sinusoidal; or (c) perivenular fibrosis; or new onset bridging fibrosis without an alternative explanation (e.g. biliary strictures) that is reasonably prevalent and not readily explained by a possible sampling error.
Arteries	Any evidence of foam cell or obliterative arteriopathy

*Patients with underlying AIH, HCV, PBC, or PSC are excluded⁴.

**Fibrosis should be graded as follows⁶⁷:

- **Portal/periportal: 0 – 3**

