In one study intended to evaluate the long-term histological outcome of immunosuppression withdrawal in liver transplant recipients, protocol liver biopsies were performed in 29 operationally tolerant living liver transplant recipients at an average of 121.2 months after liver transplantation⁸¹. Results were compared to those of recipients under maintained on immunosuppression (52 months after transplantation). The authors found that grafts from operationally tolerant recipients exhibited more fibrosis, ductular reactions and decreased luminal diameter of bile ducts as compared to patients receiving immunosuppression, and that these abnormalities improved after reintroduction of low dose immunosuppression. However, these data should be cautiously interpreted given the substantial difference in the post-transplant interval between the two groups. In addition, in six out of seven patients, improvement in fibrosis following immunosuppression reintroduction was restricted to one point of Ishak's fibrosis score, which lies within the range of potential sampling error. Of potential relevance to the current trial are the recent results of [name] et al. These investigators found that in carefully monitored studies^{16,82} no histological damage has been observed after at least 3-year follow-up post withdrawal.

Given the shortage of histological data on operational tolerance patients, it is clear that more studies are needed in order to determine the consequences of chronic absence of immunosuppression therapy. It should therefore be considered mandatory to perform liver biopsies before immunosuppression withdrawal is attempted in order to detect the development of histological abnormality, in the presence or absence of new liver function test abnormalities.

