5. STUDY SUBJECTS

5.1. Disposition of Subjects

The disposition of all enrolled subjects will be summarized in a table and listed. The information will also be presented in a consort diagram as outlined below.

The numbers and percentages of subjects enrolled, screen failures, and those that initiated withdrawal, including details of withdrawal status, will be presented. The numbers and percentages of those who complete the study or are lost to follow-up will also be presented. Additionally, reasons for early termination from the study and the reasons for discontinuing withdrawal will be presented.

* Histology instability includes biopsy results that show no rejection per Banff, but show the presence of at least one of the histological findings in Table 1.

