7.2.1. Computation of the Primary Endpoint

A participant will be considered operationally tolerant if they have successfully withdrawn from all immunosuppression and remain off all immunosuppression for 52 weeks, have no evidence of rejection since enrollment, and have a liver biopsy at 52 weeks read centrally that shows both

the absence of rejection and has histological stability consistent with Table 1. Otherwise, the participant will be considered non-tolerant.

Participants who are non-evaluable at 52 weeks following discontinuation of all immunosuppression time point due to inadequate follow-up, lack of biopsy, or premature study termination will be considered non-tolerant for the purpose of evaluating the primary endpoint.

Biopsy results may be as early as 44 weeks following the discontinuation of all immunosuppression. This is because a for-cause liver biopsy visit that occurs within 8 weeks prior to a scheduled protocol visit takes the place of a scheduled protocol visit, thus a for-cause biopsy within 8 weeks of Visit 204 can be evaluated for the primary endpoint. Any biopsies done earlier than 44 weeks prior to discontinuation of all immunosuppression will be reviewed for inclusion by the SMT on a case by case basis. Any primary endpoint biopsy performed later than 52 weeks (+4 weeks) will be utilized.

All immunosuppression dosing information is collected as a daily record. Therefore, any immunosuppression information will not have an associated window.

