The incidence and progression of graft fibrosis in tolerant versus non-tolerant patients.	
Fibrosis will be looked at in two ways—by ISHAK ITT, PP and LAFSc.
 
ISHAK is a measure taken directly from the central pathology read.
 
LAFSc is calculated as the sum of three measures that summarize fibrosis in the portal tract (portal_fibrosis per central read), sinusoids (disse_fibrosis per central read), and centrilobular vein (central_fibrosis per central read).
 
For both ISHAK and LAFSc, a subject will be considered as having graft fibrosis if the score is greater than or equal to 2.
 
Incidence of graft fibrosis will be summarized descriptively with a proportion and corresponding two-side 95% exact binomial confidence interval using Ishak Score and LAFSc, separately, for tolerant and non-tolerant subjects.
 
Change in ISHAK score from baseline biopsy to the last available biopsy will be calculated. Descriptively statistics will be calculated separately for tolerant and non-tolerant subjects. This same process will be repeated for LAFSc.
 
All scores utilized will be from the central read.

The incidence of graft loss.	Proportion of participants who have lost their liver graft with a corresponding two-sided 95% exact binomial confidence interval. ITT, PP
The incidence of all-cause mortality.	Proportion of participants who have died with a corresponding two-sided 95% exact binomial confidence interval. ITT, PP

The incidence of study-related SAEs.	Proportion of study-related SAEs as assessed by the NIAID Medical Monitor with a corresponding two-sided 95% exact binomial confidence interval.	ITT, PP
Efficacy		
The proportion of operationally tolerant subjects who remain free of rejection at 3 years after completing immunosuppression withdrawal.	Proportion of tolerant participants who remain off all IS and free of rejection 3 years after completing immunosuppression withdrawal with a corresponding two-sided 95% exact binomial confidence interval.	Tolerant Subjects

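### The tolerant v non-tolerant fibrosis table conditions on its own outcome: marked week-52 fibrosis in off-drug completers is counted outside the tolerant column

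*SAP*

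**What the plan says.** **Group definition.** Protocol 3.3.1 and SAP 7.2.1 call a participant tolerant only if the centrally read week-52 biopsy shows no rejection and none of the Table 1 findings. The fibrosis row of Table 1 reads "Greater than 1 grade increase in fibrosis in any one compartment: (a) portal/periportal; (b) peri-sinusoidal; or (c) perivenular fibrosis", or new bridging, with allowance for sampling error and other causes. For everyone else the SAP says "Otherwise, the participant will be considered non-tolerant". Protocol 6.9 adds that a Table 1 finding does not oblige a restart of immunosuppression but still counts as failed withdrawal.

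**Outcome.** SAP Table 7-2 uses the Ishak score and LAFSc, both from the central read: "LAFSc is calculated as the sum of three measures that summarize fibrosis in the portal tract", the sinusoids and the centrilobular vein. Incidence is a score of 2 or more. Progression is the change from the baseline biopsy to the last one available. On presentation: "Descriptively statistics will be calculated separately for tolerant and non-tolerant subjects".

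**Biopsy schedule.** Appendix 2 (completed withdrawal) has protocol biopsies at weeks 52 and 156. Appendix 3 (withdrawal started but not completed) has none.

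**Related text.** The footnote to the disposition diagram in SAP 5.1 defines a separate class: "Histology instability includes biopsy results that show no rejection per Banff" but at least one Table 1 finding. The Graft Fibrosis shell has only tolerant, non-tolerant and total columns.

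**The concern.** The three Table 1 fibrosis compartments (portal/periportal, peri-sinusoidal, perivenular) are the three LAFSc components, and both come from the central read. Part of the outcome therefore decides which column a participant enters. Someone who completed withdrawal, never rejected, is off drug and has a two-grade rise at week 52 goes into the non-tolerant column, beside people who resumed immunosuppression.

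Fibrosis is a listed safety endpoint, and how grafts fare off drug is a question the protocol itself leaves open. After describing one study with more fibrosis in tolerant grafts (which it says to read cautiously, because the post-transplant intervals differed) and others with no histological damage at three years or more, Protocol 3.4 concludes: "it is clear that more studies are needed in order to determine the consequences of chronic absence of immunosuppression therapy". A table that takes the worst week-52 off-drug cases out of the tolerant column cannot answer that, and a reader may take that column as the off-drug result.

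**Working it through.** **1. The plan's own figure.** Protocol 9.3 takes 40% tolerance in 60 participants: 24 tolerant, 36 not. The exact 95% interval for 24/60 is 27.6% to 53.5%, as stated. Neither document gives a fibrosis rate or a size calculation for this endpoint, so everything below is illustrative.

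**2. Counts.** Let k rejection-free, off-drug completers fail on the fibrosis criterion alone, with 24 tolerant. Setting aside rises excused by sampling error or another cause, none of the 24 has a rise above one grade at week 52, whatever k is. Among all off-drug completers the share is k/(24 + k):

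- k = 2: 2/26 = 7.7%
- k = 4: 4/28 = 14.3%
- k = 6: 6/30 = 20.0%
- k = 8: 8/32 = 25.0%

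This share is not a row in the planned shell; it shows who has been removed from the column.

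**3. Week-52 mean LAFSc change with no true group difference.** Assume 55% fail by rejection and, by week 52, each compartment independently rises one grade with probability p1 or two with p2. Take p1 = 0.10, p2 = 0.03.

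- True mean in everyone: 3 × (0.10 + 2 × 0.03) = 0.48.
- Probability of no two-grade rise: 0.97³ = 0.9127.
- Tolerant mean: 3 × 0.10/0.97 = 0.309.
- Fibrosis-failure mean: (0.48 − 0.9127 × 0.309)/0.0873 = 2.26.
- Shares of the trial: tolerant 0.45 × 0.9127 = 0.411; fibrosis failures 0.45 × 0.0873 = 0.039; rejection 0.55.
- Non-tolerant mean: (0.55 × 0.48 + 0.039 × 2.26)/0.589 = 0.60.

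So 0.31 v 0.60 appears where the truth is 0.48 in both. Across assumed p1/p2 from 10%/1% to 20%/8%, simulation gave 0.30 v 0.40 up to 0.65 v 1.31. Regrouping as all rejection-free completers v rejection removed the gap (0.36 v 0.36 up to 1.08 v 1.08).

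**4. The planned measure runs to the last biopsy.** Let the same expected change (0.48) occur again between weeks 52 and 156, ignoring the grade ceiling. The tolerant mean is 0.309 + 0.48 = 0.79 and the fibrosis-failure mean is 2.26 + 0.48 = 2.74.

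- If everyone had a year-3 biopsy, the non-tolerant mean would be (0.55 × 0.96 + 0.039 × 2.74)/0.589 = 1.08, higher than 0.79.
- But participants who fail before completing withdrawal have no protocol biopsy. Suppose all rejection failures are of this kind and their last biopsy is for-cause, with half the week-52 change (0.24). The non-tolerant mean is then (0.55 × 0.24 + 0.039 × 2.74)/0.589 = 0.41, lower than 0.79.
- The sign turns where the early failures' mean change is (0.589 × 0.79 − 0.039 × 2.74)/0.55, about 0.65.

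The same null therefore gives either direction, depending on when early failures were last biopsied.

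**5. What stays in the tolerant column.** One grade up in all three compartments (LAFSc +3) is compatible with tolerance, as is any fibrosis arising after week 52.

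**The case against.** A reader might infer that the table is circular outright: tolerant participants look protected by definition, whatever being off drug does. The documents do not support that. The criterion is more than one grade in one compartment, or new bridging, at week 52. The planned measures are a score of 2 or more and change to the last biopsy, due at week 156 for completers, and Ishak is not the Table 1 scale. The week-52 gap in step 3 is not a contrast the SAP reports, and step 4 shows that differential biopsy timing can reverse the sign. These limits stand, and they are why the point is bias rather than a foregone result.

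It can also be said that off-drug fibrosis is not hidden: such a participant fails the primary endpoint, the disposition diagram has a class for histology instability, and the shell has a total column. This stands in part. The class covers every Table 1 finding, the total mixes in participants back on drug, and neither shows fibrosis in off-drug completers.

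Finally, Protocol 3.3.2 names the tolerant v non-tolerant contrast and the SAP carries it out faithfully, as a descriptive summary of one secondary endpoint. That is fair. It is a reason to keep the split and qualify it, not to replace it.

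**Conclusion.** The concern holds in limited form. From the definitions alone, with no simulation, week-52 fibrosis helps define the groups being compared on fibrosis, and marked off-drug fibrosis at week 52 is removed from the tolerant column. As a description of off-drug fibrosis, that column is too favourable.

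The size rests on rates the documents do not give. With 24 tolerant and 2 to 8 fibrosis-only failures, the week-52 share among off-drug completers would be 7.7% to 25%, against 0% among the tolerant (excused rises aside). The net direction of the planned change-to-last-biopsy comparison is not established, so it should not be said that the table will favour the tolerant group.

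The contrast is not evidence on the effect of being off drug. Protocol 9.2.2 provides t-tests and chi-squared tests between these groups while SAP Table 7-2 is descriptive; a p-value here would have no clear meaning. This is a worthwhile improvement to one descriptive secondary safety endpoint and does not threaten the primary analysis.

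**What to change.** - Keep the tolerant v non-tolerant split named in the protocol. Footnote it as conditioned on week-52 fibrosis and not evidence on the effect of being off drug. Attach no p-value.
- Add to Table 7-2 and the Graft Fibrosis shell a column for all participants who completed withdrawal and were rejection-free and off immunosuppression at the week-52 biopsy, regardless of Table 1.
- Within it, show histology instability separately and, inside that class, those who met the fibrosis criterion.
- For that column, report change from baseline to week 52 and from week 52 to week 156, for both scores.

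The addition does not make the remaining participants a like-for-like comparator, since those who failed early still lack protocol biopsies; its value is a less biased description of fibrosis off drug. The cost is SAP text and one more column, with any SAP amendment review that Protocol 9.5 calls for. No new data are needed. The off-drug fibrosis figure will probably look less favourable.
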